4.6 Definitions of Dose-Limiting Toxicity (DLT)

All AEs of the specified grades should count as DLTs except those that are clearly and incontrovertibly due to disease progression or extraneous causes.

1. Hematological toxicity:

- CTCAE Grade ≥ 4 thrombocytopenia;
- CTCAE Grade 4 neutropenia lasting >7 days;
- CTCAE Grade ≥ 3 febrile neutropenia, where Grade 3 febrile neutropenia is defined as ANC $<1000/\text{mm}^3$ and a single temperature of $>38.3^\circ \text{C}$ (101°F) or a sustained temperature of $\geq 38^\circ \text{C}$ (100°F) for more than one hour;
- CTCAE Grade 3 thrombocytopenia ($\geq 25,000/\text{mm}^3$ and $<50,000/\text{mm}^3$) associated with bleeding;
- CTCAE Grade 4 ($<25,000/\text{m}^3$) thrombocytopenia lasting >5 days;

2. Non-hematological toxicity:

- Hy's law, defined as:
 - ✧ AST or ALT > 3 x the upper limit of normal (ULN) AND
 - ✧ Total bilirubin > 2 x ULN AND
 - ✧ Alkaline phosphatase < 2 x ULN AND

- ◇ No other reason for liver injury
- ALT or AST >8x ULN, ALT or AST >5x ULN for more than 2 weeks, ALT or AST >3x ULN and (TBL >2x ULN or INR >1.5)
 - ◇ For patients with hepatic metastases, AST or ALT > 8 x ULN or AST or ALT > 5 x ULN for \geq 14 days
- Grade > 3 non-hematologic toxicity with the exception of the following
 - ◇ Grade 3+ fatigue \geq 7 days regardless of baseline Grade;
 - ◇ Grade 3 nausea and vomiting, lasting \leq 2 days with optimal medical management;
 - ◇ Grade 3 diarrhea lasting \leq 3 days with optimal medical management
 - ◇ \geq 3+ non-hematologic abnormalities should also include laboratory values that cause symptoms.

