1.5 Clinical Study Compliance

This study will be conducted in compliance with this protocol, Good Clinical Practice (GCP), and all applicable regulatory requirements in United States

2 Objectives

Primary Objective:

- Establish the recommended phase II dose (RP2D) and/or the maximum tolerated dose (MTD) of FWD1802 as monotherapy and in combination with palbociclib in patients with ER+/HER2- unresectable locally advanced or metastatic breast cancer
- Explore the safety and tolerability of FWD1802 as monotherapy and in combination with Palbociclib

Secondary Objective:

- Characterise Pharmacokinetics of FWD1802 as monotherapy and in combination with palbociclib
- Explore preliminary efficacy signals

Exploratory Objective:

- Biomarker of FWD1802 as monotherapy and in combination with palbociclib

3 Endpoints

Safety should be evaluated at follow-up visits and throughout the study. Adverse events will be assessed for their severity (based on the NCI-CTCAE 5.0 rating), duration, and association with study treatment.

The following safety indicators will be measured and evaluated at designated intervals throughout the study. Patient history was taken at baseline to understand underlying conditions.

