4.4 Dose Escalation/Stopping Criteria

The combination of ‘accelerated escalation’ and the traditional ‘3+3’ was used for Part A study. It’s planned that one eligible subject will be enrolled for the evaluation of the first

dose levels (25 mg) using intra-individual dose escalation, when it is approved by sponsor and investigator. If no \geq grade 2 adverse event (defined as any \geq grade 2 adverse event occurs during the DLT observation period unless it is clearly related to disease progression or extraneous cause) occurs during the DLT observation period, dose escalation enters the 2nd dose group with the traditional '3+3' mode. Otherwise, additional 2 subjects will be added to the current dose group, and the dose group and subsequent dose groups will switch to a '3+3' dose escalation design. Before starting the next dose level, all subjects (n=1, 3, or 6) at the current dose level must complete the DLT observation period and be determined by the Safety Monitoring Committee (SMC) to proceed to the next dose level. If no DLT has occurred at the end of the DLT observation period, subjects may adjust its dose level to any higher dose level that no DLT events have occurred during the DLT observation period, as assessed by the investigator and determined by the SMC, and on the condition that the investigator considers safe for the subjects.

If MTD cannot be determined at this part due to too few DLT events, a higher dose or an intermediate dose can be explored as needed, after the dose escalation reaches the highest predicted dose or is determined by the SMC.

The traditional '3+3' increment rule for dose escalation is as follows:

- The dose will be escalated if no DLT has been reported in the first 3 subjects of this dose group after DLT observation period.
- If 1 of the first 3 subjects enrolled has DLT occurred, then 3 additional subjects will be enrolled, with totally 6 subjects in this dose group.

-If only 1 DLT event occurs in these 6 subjects, then the dose will be escalated.

-If ≥ 2 DLT events occur in these 6 subjects, then no more subjects will be enrolled in this dose group and the dose escalation will be stopped. The SMC will decide whether to use the intermediate dose as the next dose level for the study or to terminate the dose escalation.

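### The sustained-fever limit in the febrile-neutropenia DLT is printed as 38 °C with 100 °F beside it; 38 °C is 100.4 °F, so one criterion carries two cut-offs.

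*Protocol*

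**What the plan says.** Section 4.6 of the protocol lists, among the haematological DLTs, grade 3 or higher "febrile neutropenia, where Grade 3 febrile neutropenia is defined as ANC" below 1000/mm³ together with one of two temperature conditions:

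- a single temperature above 38.3 °C, with the Fahrenheit value given as "101°F) or a sustained temperature of" (the quoted words run on into the second condition);
- a sustained temperature of at least 38 °C, with the Fahrenheit value given as "100°F) for more than one hour".

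The DLT definition in the synopsis prints the same two pairs. The protocol nowhere gives 100.4 °F, and it does not say which unit takes precedence.

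Section 4.4 sets out what a DLT does. On the first DLT: "If 1 of the first 3 subjects enrolled has DLT occurred, then 3 additional subjects will be enrolled". If two or more DLTs occur among the six, "then no more subjects will be enrolled in this dose group and the dose escalation will be stopped". Section 4.5 defines the MTD as the highest dose level with a DLT incidence below 33%.

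**The concern.** The two figures in the sustained-fever condition are meant to be the same limit in two units, and they are not. A subject with a low neutrophil count and a mild sustained temperature can be classified differently depending on which figure the site reads. This limit is a decision threshold, because section 4.6 counts every listed event as a DLT unless it is clearly due to progression or an extraneous cause.

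Section 1.5 places the study under "all applicable regulatory requirements in United States", so some sites may record temperature in Fahrenheit. That is an assumption: the protocol does not state the unit in which temperature is recorded. If it holds, such a site could apply the lower limit.

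The point bears most on Part B, where the drug is combined with palbociclib. Table 6 reports neutropenia of grade 3 in 55% and of grade 4 in 11% of patients on fulvestrant plus palbociclib. Low counts are therefore expected there, and the temperature limit can become the condition that decides.

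**Working it through.** **Inputs.** Sustained limit 38 °C, printed with 100 °F, and single-reading limit 38.3 °C, printed with 101 °F (section 4.6 and the synopsis). Escalation rule from section 4.4; MTD definition from section 4.5.

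**Formulas.** F = C × 9/5 + 32 and C = (F − 32) × 5/9.

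**Reproducing the printed figures.**

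| Limit | Exact conversion | Printed | Printed minus exact |
|---|---|---|---|
| Single reading, 38.3 °C | 38.3 × 9/5 + 32 = 100.94 °F | 101 °F | +0.06 °F |
| Sustained, 38 °C | 38 × 9/5 + 32 = 100.4 °F | 100 °F | −0.4 °F |

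Both printed values match rounding to a whole degree (100.94 to 101, and 100.4 to 100). The exact equivalent of 38 °C is not reproduced.

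**Size of the gap.** 100 °F = (100 − 32) × 5/9 = 37.78 °C, which is 0.22 °C below the Celsius limit.

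**Readings affected.** The limit includes equality, so a reading of exactly 100.0 °F meets the printed Fahrenheit value. On a scale read to 0.1 °F, the disputed readings run from 100.0 to 100.3 °F. Since (100.3 − 32) × 5/9 = 37.94, that is 37.78 to 37.94 °C. They meet the Fahrenheit limit and miss the Celsius one.

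**Effect of one added DLT under section 4.4.**

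- 0/3 becomes 1/3: three more subjects are enrolled instead of the dose being escalated.
- 1/6 = 16.7% becomes 2/6 = 33.3%: escalation stops at that level, and the level no longer meets the below-33% definition of the MTD.

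These are the consequences if such an event occurs. They do not say how often it would.

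**The case against.** The strongest reply is that this is rounding and not a faulty conversion. Both Fahrenheit values are whole degrees and both are correctly rounded. Celsius comes first, the Fahrenheit figure is only in brackets, and the protocol's storage temperatures are given in Celsius alone. A site that records in Celsius meets no ambiguity.

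The route to a wrong classification is also narrow. It needs ANC below 1000/mm³, a reading held for more than an hour inside a 0.4 °F band, no higher reading that would qualify anyway, a site that applies the bracketed figure, and onset within the evaluation window (34 days in Part A, 28 days in Part B). Section 1.4.1 gives febrile neutropenia in 0.9% of patients on fulvestrant plus palbociclib, over a median of 10.8 months of treatment. For the 12 patients planned in Part B, 12 × 0.009 is about 0.1 events over the whole treatment time. On fulvestrant plus placebo, neutropenia of any grade was 4%. The change from 1/6 to 2/6 would follow from any added DLT and does not measure the effect of this one.

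Most of this stands, and it is why the point ranks as minor. The 0.9% is only a rough guide: it comes from a different drug and counts febrile neutropenia itself, not the readings just below the limit. Rounding explains the figure but does not make the two limits equal. It is nearly harmless in the first pair (0.06 °F) and moves the second by 0.4 °F, and the text does not say that the bracket is approximate.

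**Conclusion.** The point holds and is minor. The printed Fahrenheit limit is 0.4 °F (0.22 °C) below the Celsius limit that it should equal, in section 4.6 and in the synopsis alike. The arithmetic needs no assumption. A practical effect does need one, namely that some sites read or record in Fahrenheit and apply the bracketed value.

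The direction is conservative: the lower figure can add a DLT but cannot cause a qualifying sustained fever to be missed. The protocol gives no rate for sustained readings of 100.0 to 100.3 °F with ANC below 1000/mm³, so no frequency is claimed, and the effect is expected to be small. The planned sample size and the analyses are unaffected. It deserves correction because it is a threshold feeding the escalation rule and the MTD, where a single event can change the decision.

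**What to change.** Print the sustained limit as at least 38 °C (100.4 °F) in section 4.6 and in the DLT definition of the synopsis. Giving Celsius alone would also remove the conflict. The cost is one figure in two places, with no change to the design; it can go into the next amendment.

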3.1 Safety and Tolerability

- Incidence of DLT in the MTD evaluation period, adverse events, treatment emergent adverse event (TEAE), serious adverse event (SAE), their relationship with the investigational product and respective severity.
- Changes in vital signs, ECOG score, ECG, physical examination, and laboratory tests before and after treatment, and the use of concomitant medication.

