4.5 Definition of MTD

- The maximum tolerable dose (MTD) is defined as the highest dose level while the incidence of DLT is less than 33% in the dose escalation study during the DLT evaluation period.
- Six patients are required to establish the MTD. If only 3 patients have been evaluated in the previous dose level below the non-tolerated dose, the cohort should be expanded to 6 patients at the previous dose level below the non-tolerated dose. If DLT is not observed in the additional 3 patients, or 6 patients have been evaluated at the previous

dose level, the MTD will be confirmed at the previous dose level below the non-tolerated dose.

- If MTD is not established at the end of escalation, the maximum safety dose will be defined as the maximum administrated dose (MAD).
- The recommended dose for expansion(s) will be confirmed comprehensively based on the results of safety, tolerability, PK and PD. The RP2D should be a pharmacologically active dose and the dose should be selected by pooling and evaluating all available PK, PD, target engagement, efficacy, safety, and tolerability data to select the appropriate dose. There will need to be at least 6 patients at the recommended dose for expansion level(s) to evaluate the safety, PK, PD and tolerability. If the DLT does not occur during the DLT assessment period, the current highest dose level will not be considered as the basis of dose escalation and may be used as a reference to dose design and safety evaluation of the recommend dose.

Based on the safety data, a higher dose level beyond dose level 9 or an intermediate dose level can be explored as determined by the SMC.

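### The general non-hematologic DLT rule contradicts itself: it counts only Grade > 3 yet exempts short Grade 3 events, and it exempts prolonged rather than brief fatigue

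*Protocol*

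**What the plan says.** Section 4.6 lists hematologic DLTs, then separate liver criteria (Hy's law and ALT/AST multiples of ULN, one of them "ALT or AST >5x ULN for more than 2 weeks"), then a general rule: "Grade > 3 non-hematologic toxicity with the exception of the following". Four items stand under that rule:

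1. Grade 3+ fatigue lasting at least 7 "days regardless of baseline Grade";
2. "Grade 3 nausea and vomiting, lasting" no more than 2 days with optimal management;
3. "Grade 3 diarrhea lasting" no more than 3 days with optimal management;
4. a sentence that Grade 3 or higher "non-hematologic abnormalities should also include laboratory values that cause symptoms".

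The synopsis prints the same rule and the same four items. Nothing elsewhere in the protocol corrects them.

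The definition has several uses. Section 3.1 lists "Incidence of DLT in the MTD evaluation period" as an endpoint. Section 4.5 defines the MTD as "the highest dose level while the incidence of DLT is less than 33"%. Section 4.4 sets each 3+3 step by the DLT count and makes the absence of a DLT one condition for moving a patient to a higher dose. Section 2 makes the RP2D and/or MTD a primary objective.

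**The concern.** The rule has three defects.

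- **Threshold.** Grade 3 is not above Grade 3, so items 2 and 3 remove nothing from a Grade > 3 rule. They make sense only if the threshold is Grade ≥ 3.
- **Fatigue.** Items 2 and 3 exempt short events, while item 1 exempts long ones. It is either an exception with its duration reversed or an inclusion put in the wrong list. The text does not say which.
- **Laboratory values (secondary).** Item 4 is worded as an inclusion but sits among the exceptions. The rule does not say whether asymptomatic Grade ≥ 3 values are exempt.

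Section 4.6 counts every AE of a specified grade unless it is clearly due to progression or an extraneous cause, so the grade cut-off decides the classification. Sites that read the rule differently will classify the same event differently. The difference carries into the escalation step, the reported DLT incidence and the MTD.

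**Working it through.** The plan states no figure to reproduce. The check is a reading of the text, followed by an illustration of the consequence.

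**Is the symbol a text-extraction loss?** Unlikely. Grade > 3 appears identically in section 4.6 and the synopsis, and ≥ survives in neighbouring lines (the 7-day and 14-day conditions and item 4). If the source did read ≥ 3, the fatigue and laboratory defects would remain.

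**Classification under three readings**

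| Event in the DLT window | Literal (> 3) | Only the symbol changed to ≥ 3 | Threshold and fatigue both corrected |
|---|---|---|---|
| Grade 3 rash | not a DLT | DLT | DLT |
| Grade 3 diarrhea, 10 days | not a DLT | DLT | DLT |
| Grade 3 diarrhea, 2 days | not a DLT | not a DLT | not a DLT |
| Grade 3 fatigue, 3 days | not a DLT | DLT | not a DLT |
| Grade 3 fatigue, 20 days | not a DLT | not a DLT | DLT |

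The middle column shows that a one-character correction is not enough. It could also let the general rule override the duration condition that the liver criteria set for ALT/AST.

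**Effect on one cohort.** Suppose 2 of 3 patients have Grade 3 rash. The literal text gives 0/3 DLTs and section 4.4 permits escalation. The reading implied by the exceptions gives 2/3 and section 4.4 stops it.

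**Effect on the 3+3 rule.** Section 4.4 escalates on 0/3 or 1/6 DLTs. With per-patient DLT probability p,

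P(escalate) = (1−p)³ + 3p(1−p)² × (1−p)³.

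The inputs are assumptions, because the protocol gives no DLT rate for this drug: a base rate of 5% or 10% from all other criteria, plus 1%, 2% or 5% from non-exempt Grade 3 events. With independent events, p = 1 − (1 − base)(1 − added).

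| Added | p (base 5%) | P(escalate) | Drop | p (base 10%) | P(escalate) | Drop |
|---|---|---|---|---|---|---|
| 0 (literal) | 0.0500 | 0.973 | – | 0.100 | 0.906 | – |
| 1% | 0.0595 | 0.963 | 1.0 points | 0.109 | 0.891 | 1.5 points |
| 2% | 0.0690 | 0.952 | 2.2 points | 0.118 | 0.875 | 3.1 points |
| 5% | 0.0975 | 0.910 | 6.3 points | 0.145 | 0.824 | 8.2 points |

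If the added events fall only in patients without another DLT (p = base + added), the drops are 1.1 to 1.7, 2.3 to 3.5 and 6.7 to 9.2 points. If they fall only in patients already counted, the drop is 0.

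**Rough context for the added rate.** In Table 6, the Grade 3 non-hematologic rows for fulvestrant plus placebo sum to 3 (infections) + 1 (appetite) + 1 (nausea) + 1 (diarrhea) + 1 (vomiting) + 1 (fatigue) = 8%, or 5% without nausea, vomiting and diarrhea. Median treatment was 4.8 months, about 146.1 days. At a constant rate, the 34-day Part A window gives 34/146.1 × 8% = 1.9% and 34/146.1 × 5% = 1.2%. This bounds nothing: it is another drug, the table lists only reactions with at least 10% incidence, and overlap within patients is unknown.

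**The case against.** The strongest reply is that the intent can be inferred. Two Grade 3 exceptions, the Grade 3+ in the fatigue line and the ≥ 3+ in the laboratory line all point to Grade ≥ 3, so many sites would apply that. This is fair, and it makes the fully literal reading less likely in practice. But a site that makes this correction still has the reversed fatigue line. For Grade 3 fatigue, the reversal takes effect only once the threshold is read as ≥ 3. If item 4 is taken as an inclusion, symptomatic Grade 3 laboratory values might count even on the literal text. Its place among the exceptions leaves that unclear, and it does not help with rash, diarrhea or fatigue.

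There are also real safeguards:

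- The Safety Monitoring Committee decides each step (4.2.1, 4.4). For the Part B starting dose it looks at non-DLT adverse events too (4.2.2).
- RP2D selection uses all safety and tolerability data (4.5).
- At dose level 1, any Grade ≥ 2 event not clearly due to progression or an extraneous cause triggers expansion (4.4).
- Table 9 stops treatment for symptomatic Grade 3 events, and section 4.7.3 allows suspension from Grade 2.
- Moving a patient to a higher dose also needs the investigator's and the committee's agreement.

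These can prevent an unsafe escalation. They do not make sites classify the same event alike, and they do not correct the DLT incidence or the MTD derived from it.

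Finally, the probabilities are modest at the rates suggested by Table 6: about 1 to 3.5 points for an added 1% to 2%. For Part B, the Grade 3 non-hematologic rows for fulvestrant plus palbociclib sum to about 9% over a median 10.8 months (about 328.7 days), or 28/328.7 × 9% = 0.8% per 28-day window. That stands, and the case does not rest on the probabilities.

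**Conclusion.** The concern holds and should be fixed before the next cohort decision. As written, the rule excludes Grade 3 non-hematologic events that its own exceptions imply it should count, and it exempts prolonged fatigue. A single cohort can move between 0/3 and 2/3 DLTs depending on the reading. The average effect on a 3+3 step is illustrative: a drop of about 1 to 8 points in the chance of escalating, for 1% to 5% added independent events on a 5% or 10% base, and none if the added events occur only in patients already counted. Confidence is high, because the contradiction is in the text, appears in two places and needs no assumed rate. The point on asymptomatic laboratory values is secondary and would not justify an amendment alone.

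**What to change.** Amend section 4.6 and the synopsis identically, with the clinical team confirming each choice:

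- **Threshold.** Set the general rule at Grade ≥ 3, and state that ALT/AST elevations are judged only by the separate liver criteria.
- **Fatigue.** Make prolonged fatigue count. Either exempt Grade 3 fatigue lasting less than 7 days, or move the existing line out of the exceptions as an inclusion and exempt shorter Grade 3 fatigue.
- **Laboratory values.** Move the sentence out of the exception list. State that Grade ≥ 3 abnormalities count when they cause symptoms, and say whether asymptomatic ones are exempt.

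If Grade > 3 is truly intended, delete the empty Grade 3 exceptions and still remove the exemption of prolonged fatigue.

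The cost is an amendment to one rule in two places and three recorded clinical decisions (threshold, fatigue, asymptomatic laboratory values). No extra patients, visits or procedures are needed.

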4.7 Dose modifications

4.7.1 Dose Reductions

Dose reductions will be only allowed beyond DLT evaluation period in the dose escalation and expansion studies. Subjects who experience the unacceptable adverse events may continue treatment at the next lower dose level until disease progression or unacceptable toxicity. Adverse events considered for dose reduction should not include the events assessed by the investigator as exclusively related to underlying disease or other medical condition or concomitant treatment. The dose reduction guideline for general adverse events are outlined in Table 9. Provisions are not made for dose levels below 25 mg. If 25 mg once daily is determined to be unsuitable based on DLT as defined above, FWD1802 will be permanently discontinued.

Table 9 Dose reductions guideline for general adverse events

CTCAE grade	Follow-up procedures and dose reductions
CTCAE grade 1	Continue to receive study treatment at same dose level Monitor closely. Provide supportive therapy.
CTCAE grade 2	Discontinue study treatment if there are clinical symptoms. Monitor closely. Provide supportive therapy. Restart study treatment at the same dose level if resolved to CTCAE grade 1 or baseline within 14 days.
CTCAE grade 3	Discontinue study treatment if there are clinical symptoms. Monitor closely.

CTCAE grade	Follow-up procedures and dose reductions
CTCAE grade 4	Provide supportive therapy. Restart to study treatment at one dose level lower (except dose group 1) if resolved to CTCAE grade 1 or baseline. Discontinue treatment if CTCAE grade 3 AE occurs again. Restart to study treatment at one dose level lower if resolved to CTCAE grade 1 or baseline within 21 days. Discontinue study treatment if there are clinical symptoms. Monitor closely. Provide supportive therapy. Restart to study treatment at one dose level lower (except dose group 1) if resolved to CTCAE grade 1 or baseline within 21 days. If CTCAE grade 4 AE occurs again, discontinue permanently based on investigator and sponsor's judgement.

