4.7.3 Temporary Withdrawal

Study treatment may be suspended (not more than 28 days) for any of the following treatment-related adverse events: Grade 2 or higher adverse events, if clinically indicated, study treatment should be suspended until the event returns to grade 1 or baseline levels (see Table 9)

The study drug may be discontinued for no more than 28 days until toxicity is relieved, or based on the investigator's judgment. If > 28 days, the patient continues to benefit from the treatment as assessed by the investigator, the patient may continue to receive the study treatment.

5 Study Population

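### Above 25 mg, no rule makes a dose hold mandatory for a first laboratory-defined DLT without symptoms, because Table 9 ties interruption to clinical symptoms

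*Protocol*

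**What the plan says.** Protocol section 4.7.1, Table 9, sets out what to do with study drug after an adverse event of each CTCAE grade. The rows for Grades 2, 3 and 4 all carry the instruction "Discontinue study treatment if there are clinical symptoms", together with close monitoring and supportive therapy, which have no symptom condition. After recovery, the restart for Grades 3 and 4 is one dose level lower. For repeat events the table is firmer: "Discontinue treatment if CTCAE grade 3 AE occurs again". A repeat Grade 4 event leads to permanent discontinuation on the judgement of the investigator and sponsor.

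The same section restricts reductions by time: "Dose reductions will be only allowed beyond DLT evaluation period in the dose escalation and expansion studies". It contains one dosing rule tied to a DLT in an individual patient: "If 25 mg once daily is determined to be unsuitable based on DLT as defined above, FWD1802 will be permanently discontinued".

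Section 4.6 lists the DLTs. Among them are Grade 4 thrombocytopenia, "CTCAE Grade 4 neutropenia lasting >7 days", "ALT or AST >8x ULN, ALT or AST >5x ULN for more than 2 weeks", and the Hy's law criteria. None of these requires a symptom.

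Section 4.7.3 permits suspension for treatment-related events of Grade 2 or higher: "if clinically indicated, study treatment should be suspended until the event returns to grade 1 or baseline levels". It refers back to Table 9. Section 5.4.1 lets the investigator withdraw a patient for an unacceptable adverse event.

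**The concern.** The two sections use different thresholds for the same event. Section 4.6 treats a sufficiently abnormal laboratory value as serious enough to count against the dose level, whether or not the patient feels anything. Table 9 does not treat that value as enough to interrupt the patient's own dosing, because its trigger is symptoms. Marked liver enzyme elevation, neutropenia and thrombocytopenia are findings that a laboratory report may reveal before the patient notices them, so the symptom condition leaves out the cases that section 4.6 was written to catch.

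This is a first-in-human study. What is at stake is the safety of a patient who has already met a DLT, and consistency between sites in handling her. Section 1.4.2 says that individual stopping criteria will be specified, and a first DLT above 25 mg is an obvious place for one.

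**Working it through.** No figure in the protocol's statistics depends on this point. The check is a reading of every rule that could force a hold, followed by one count from the visit schedule.

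**Step 1. The case to test.** A patient above 25 mg, inside the DLT window, has a first event that meets section 4.6 on laboratory findings and has no symptoms.

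**Step 2. Each rule applied to that case.**

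| Rule | Trigger | Forces a hold here? |
|---|---|---|
| Table 9, Grades 2 to 4, first event | Clinical symptoms | No; monitoring and supportive care only |
| Table 9, recurrent Grade 3 | Second occurrence | No; this is a first event |
| Table 9, recurrent Grade 4 | Second occurrence, on judgement | No; this is a first event |
| 4.7.1, 25 mg rule | 25 mg unsuitable on DLT grounds | No; dose is above 25 mg |
| 4.7.1, dose reduction | After the DLT window only | No; not available yet |
| 4.7.3, suspension | Treatment-related event, if clinically indicated | No; left to judgement |
| 5.4.1, withdrawal | Investigator finds the event unacceptable | No; left to judgement |
| 4.4, 3+3 rule | DLT count in the cohort | No; governs cohort size and escalation, not her dosing |

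No row makes a hold mandatory. Because Table 9 prints the same condition for Grades 2, 3 and 4, the result does not depend on which of these grades the laboratory value falls in.

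**Step 3. The window.** Part A: 6 days of single-dose run-in + 28 days of Cycle 1 = 34 days, as stated in section 4.2.1 and the synopsis. Part B: Cycle 1, 28 days.

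**Step 4. Doses before the next scheduled test.** In Tables 1 and 2, haematology and chemistry fall on Cycle 1 Days 1, 8, 15 and 22, then Cycle 2 Day 1. The nominal gaps are 8 − 1 = 7, 15 − 8 = 7, 22 − 15 = 7 and 29 − 22 = 7 days. With once-daily dosing and no hold, 7 days × 1 dose per day = up to about 7 further full doses before the next scheduled test.

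This is a ceiling taken from the schedule alone. Close monitoring under Table 9 and the extra testing foreseen in section 1.4.2 would shorten the interval, and an investigator who suspends treatment brings the count down at once.

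**The case against.** The strongest reply is that the protocol does not leave such a patient unattended. Table 9 requires monitoring and supportive therapy whatever the symptoms. Section 4.7.3 says treatment should be suspended when clinically indicated, carries no symptom wording of its own, and applies inside the DLT window. Section 5.4.1 allows withdrawal, and few investigators would keep dosing on a known Grade 4 result. Discretionary holding can also be defended as a design choice. All of this stands, and it means that a reader who infers that no action at all is stated inside the window goes too far. It does not supply a mandatory hold.

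A reader might also infer that the section contradicts itself, since it bars reductions inside the window while the Grade 3 and 4 restart is one level lower. The text has a workable reading: the patient is held, stays off drug until the window closes, and then restarts lower. It should say so, but it is not a contradiction. Parts of the Grade 3 and 4 rows are also run together in the extracted text, so fine inference from their restart lines would be unsafe. The symptom condition itself is legible for both grades.

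Not every listed DLT is purely a laboratory reading. The Hy's law criteria also require that no other cause of liver injury is found, which is a clinical judgement. The neutropenia criterion and the lower ALT/AST criterion need persistence, so the patient has already been followed with an abnormal value before the DLT exists. These points narrow the picture, but no symptom requirement appears in any of them.

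Finally, the 14-day testing gap in Cycle 2 and the 28-day gap from Cycle 3 and throughout Part C might be used to enlarge the problem. They lie outside the DLT window, and reductions become available once the window has passed, so they do not measure this gap.

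**Conclusion.** The concern holds in a limited form. Above 25 mg, the protocol makes no hold mandatory for a first asymptomatic laboratory DLT; what it requires is monitoring and supportive care, with suspension or withdrawal left to judgement. Followed literally, the symptom condition is less protective of the patient than the DLT definition it sits beside.

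The size is at most about 7 further full doses between scheduled tests in Cycle 1 of Parts A and B. That assumes nominal visit days, daily dosing, no unscheduled test and no discretionary hold. The protocol gives no frequency for such events, so no expected number of affected patients can be stated.

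A reader might infer that the escalation decision is biased as well. The documents do not support that from this gap: an event meeting section 4.6 counts as a DLT under section 4.4 whether or not dosing continues. The consequence is for patient safety and uniform conduct across sites. It merits correction because the remedy is specific and cheap.

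**What to change.** 1. In Table 9 and section 4.7.3, require FWD1802 to be held for any event meeting section 4.6, and for any Grade 4 event, regardless of symptoms. The symptom condition can stay for other Grade 2 and 3 events.
2. State in section 4.7.1 that, because reductions are barred inside the DLT window, a patient held for a DLT stays off drug until the window ends, and then either restarts one level lower on recovery or discontinues.

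The cost is a few sentences of protocol text and an occasional interruption in a patient without symptoms. Sample size and the 3+3 rule are unchanged.
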